7.3.4 Prior Therapy

The following will be summarized:

- Number of subjects by type of prior therapy received (excluding preparative regimen for ASCT):
 - Immunotherapy by Monoclonal Antibodies
 - Steroid
 - Chemotherapy Anthracyclines
 - Chemotherapy Other than Anthracyclines
 - Kinase Inhibitors
 - Immunomodulary Derivatives
 - Radioimmunotherapy
 - Other
- Number of prior systemic regimen received (0, 1, 2, 3, ≥ 4), excluding preparative regimen for ASCT subjects
- Number of subjects per type of regimen for first and second lines of therapy (e.g. R-CHOP, ICE).For CTCL number of subjects per type of regimen by line of therapy where the combination of drugs within a regimen will be the concatenation of drugs by alphabetical order (e.g. gemcitabine)
- Number of subjects with prior ASCT and type of regimen received for preparation to ASCT (e.g. Carmustine / Cytarabine / Etoposide / Mephalan) and number of subjects ASCT ineligible.
- Best response to most recent prior regimen (CR vs. PR vs. SD vs. Relapse/PD vs. Unable to Determine vs. Not reported)
- Prior radiotherapy (yes or no)
- Prior surgery (yes or no)

By subjects will also list the systemic therapy, details about ASCT and details about surgery and radiotherapy.

7.3.5 Baseline Examinations

Percentage of subjects with abnormal baseline physical examination will be tabulated by examination criteria. A by-subject listing will also be provided.

7.4 Extent of Exposure

Analyses in this section will be performed on all treated subjects.

7.4.1 Administration of Study Therapy

The following parameters will be summarized (descriptive statistics) for each drug separately:

- Number of doses received
- Cumulative dose
- relative dose intensity
- Duration of treatment: duration of treatment will be presented using a Kaplan-Meier curve whereby the last dose date will be the event date for subjects who discontinued study therapy. Subjects who are still on study therapy will be censored on their last dose date. Median duration of treatment and associated 95% CI will be provided.

A by-subject listing of dosing of study medication (record of study medication, infusion details, dose change) and a listing of batch number will be also provided.

Below table summarizes the key parameters used to calculate dosing data.

	Nivolumab	Brentuximub Vedotin
Dosing schedule per protocol	Day 1, 240mg every 3 weeks (except cycle 1 C1D8)	1.8mg/kg (or 1.2mg/kg) every 3 weeks
Dose	Dose is defined as total dose administered. Dose administered in mg at each dosing date are collected on the CRF.	Dose (mg/kg) is defined as total dose administered (mg)/most recent weight. Dose administered in mg at each dosing date and most recent weight are collected on the CRF.
Cumulative Dose	Cum dose (mg) is sum of the doses (mg) administered to a subject during the treatment period.	Cum dose (mg/kg) is sum of the doses (mg/kg) administered to a subject during the treatment period.
Duration of treatment	Last dose date - Start dose date + 1	Last dose date - Start dose date + 1
Relative Dose intensity	If only one dose of nivolumab Cum dose (mg)/[(Last dose date of nivolumab - Start dose date of nivolumab + 14) x 240 /14] x 100	Cum dose (mg/kg)/[(Last dose date of BV - Start dose date of BV + 21) x 1.8 /21] x 100 or

Nivolumab	Brentuximub Vedotin
If more than 1 dose of nivolumab	
[Cum dose (mg) / (Last dose date of nivolumab - Start dose date of nivolumab + 21)] x [(14+(number of nivolumab doses-1) * 21 / 240 * number of nivolumab doses] x 100	

Table 7.4.1 -1: Administration of Study Therapy: Definition of Parameters

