4.3.1 Brentuximab Vedotin

Brentuximab vedotin will be administered every 21 (q 3 weeks) days by IV infusion given over approximately 30 minutes. In the absence of infusion-related reactions, the infusion rate for all subjects should be calculated in order to achieve a 30 minute infusion period. Brentuximab vedotin must not be administered as an IV push or bolus nor mixed with other medications. Brentuximab vedotin will be administered first as a 30 minute infusion followed by a minimum 30 minute rest prior to the nivolumab infusion.

Dosing is based on subject's actual body weight. Doses must be adjusted for subjects who experience a $\geq 10\%$ change in weight from baseline. Other dose adjustments for changes in body weight are permitted per institutional standard. An exception to weight-based dosing is made for subjects weighing greater than 100 kg; doses will be based on 100 kg for these individuals. Rounding is permissible within 5% of the nominal dose.

Refrigeration should be set at 2–8°C for storage of vials and solutions containing brentuximab vedotin. The controlled location must be accessible only to the pharmacist, the investigator, or a designated person. Brentuximab vedotin does not contain preservatives; therefore, opened and reconstituted vials of brentuximab vedotin should be used as soon as possible. If not used immediately, the in-use storage should not be longer than 24 hours. It is recommended that brentuximab vedotin vials and solutions be protected from direct sunlight until the time of use. Reconstituted vials and solutions must not be shaken.

Drug product vials may be labeled as brentuximab vedotin, the United States adopted name (USAN) and the International Nonproprietary Name (INN), or as SGN 35, the compound code; the 2 names can be used interchangeably.

Brentuximab vedotin vials are provided via single-use containers. Any partially used vials or diluted dosing solutions should be discarded using appropriate institutional drug disposal procedures.

Brentuximab vedotin should be reconstituted with 10.5mL of Sterile Water for Injection, United States Pharmacopeia (USP) or equivalent (see Pharmacy Binder for details) for a final concentration of 5mg/mL. The vial should be gently swirled until the contents are completely dissolved. The vial must not be shaken. The reconstituted drug product should be inspected visually for any particulate matter and discoloration.

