4.5 Selection and Timing of Dose for Each Subject

There will be 2 parts to this study. During the Dose Evaluation Phase (Cohort A) six eligible subjects will be enrolled and treated with brentuximab vedotin (IV) 1.8 mg/kg as the starting dose and may be reduced to 1.2 mg/kg if toxicities described in [Table 4.5.3-1](#) are observed. Subjects enrolled to Cohort A will be treated with a combination of brentuximab vedotin and nivolumab 240 mg flat dose (IV) of every 3 week cycle. In cycle 1, brentuximab vedotin will be administered on day 1 where as nivolumab will be administered on day 8. Subsequent to cycle 1, both drugs will be administered on the first day of the new cycle. Brentuximab vedotin will be administered first as a 30-minute infusion followed by a minimum 30-minute rest. Nivolumab will be then be administered as a 30-minute infusion

The starting dose of brentuximab vedotin 1.8 mg/kg is to be given over approximately 30 minutes intravenously. In the absence of infusion related reaction, the infusion rate for all subjects should be calculated in order to achieve a 30-minute infusion period. Dosing calculations should be based on the subject's actual body weight. If the subject's weight on the day of dosing differs by > 10% from the previous weight used to calculate the required dose, a corrected dose must be recalculated. Other dose adjustments for changes in body weight are permitted per institutional standard. All

doses should be rounded to the nearest milligram. Brentuximab vedotin may be reduced to 1.2mg/kg if toxicities described in [Table 4.5.3-1](#) are observed. The Cohort B will open with a proposed dosing regimen with cycle duration of 21 days (3 weeks). Brentuximab vedotin will be administered based on the dose identified in Cohort A (1.8 mg/kg or 1.2 mg/kg) and nivolumab will be given over 30 min intravenously at a 240 mg flat dose.

An exception to weight-based brentuximab vedotin dosing is made for subjects weighing greater than 100 kg; doses will be based on 100kg for these individuals. Rounding is permissible within 5% for the nominal dose.

There will be no dose escalations or reductions of nivolumab allowed. There are no premedications recommended for nivolumab on the first cycle. If an acute infusion reaction is noted, subjects should be managed according to [Section 4.5.6](#).

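### The SAP's brentuximab relative dose intensity ignores the protocol's 100 kg dosing cap, so subjects above 100 kg on full nominal dose score below 100%

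*SAP*

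**What the plan says.** Protocol 4.3.1 sets the brentuximab dose by actual body weight and then limits it: "An exception to weight-based dosing is made for subjects weighing greater than 100 kg; doses will be based on 100 kg for these individuals". Protocol 4.5 repeats the limit: "doses will be based on 100kg for these individuals". Section 4.3.1 also allows for vial handling: "Rounding is permissible within 5% of the nominal dose".

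SAP Table 7.4.1-1 defines the exposure variables for brentuximab in three steps.

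- Dose: "Dose (mg/kg) is defined as total dose administered (mg)/most recent weight".
- Cumulative dose: "Cum dose (mg/kg) is sum of the doses (mg/kg) administered to a subject during the treatment period".
- RDI: "Cum dose (mg/kg)/[(Last dose date of BV - Start dose date of BV + 21) x 1.8 /21] x 100".

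The same table gives the planned schedule as "1.8mg/kg (or 1.2mg/kg) every 3 weeks". It says that milligrams given and most recent weight come from the CRF. It does not say that the weight is truncated at 100 kg. SAP 7.4.1 supplies its own formulas and does not defer to the Core Safety SAP for them, and the cap appears nowhere in the SAP text.

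**The concern.** RDI should show how far delivery departed from the plan. For a subject above 100 kg the plan is a fixed number of milligrams, but the SAP scores that subject against a plan that keeps rising with weight. The numerator uses uncapped weight and the reference stays at 1.8 mg/kg, so full compliance with the protocol is recorded as a shortfall.

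What is at stake is the reading of the brentuximab exposure table. Its RDI would mix real departures (reductions, delays, omissions) with an effect of body weight, always in the direction of under-delivery for heavy subjects.

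**Working it through.** The documents state no RDI value, so there is no figure to reproduce. The check applies the SAP formula to a subject dosed as the protocol prescribes.

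**Inputs**
- Planned level 1.8 mg/kg every 21 days (SAP Table 7.4.1-1). SAP 7.1 confirms that this was the only level explored in Cohort A.
- Dosing weight: the smaller of actual weight and 100 kg (protocol 4.3.1, 4.5).
- Divisor: most recent weight, uncapped (SAP Table 7.4.1-1).

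**Formula.** Take n doses, each exactly 21 days apart, at constant weight w above 100 kg.
- Milligrams per dose = 1.8 x 100 = 180.
- SAP dose per kilogram = 180/w, and cumulative dose = n x 180/w.
- Last minus first dose date = 21(n - 1). Adding 21 gives 21n days. Multiplying by 1.8/21 gives a reference of 1.8n.
- RDI = 100 x (n x 180/w)/(1.8n) = 100 x 100/w. The number of doses cancels.

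**Check at or below the cap.** At 60, 80 and 100 kg the same calculation gives exactly 100%, so the formula behaves properly there.

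**Results above the cap, 180 mg on schedule**

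| Weight | SAP mg/kg per dose | SAP RDI | RDI with divisor capped at 100 kg |
|---|---|---|---|
| 105 kg | 1.71 | 95.2% | 100% |
| 110 kg | 1.64 | 90.9% | 100% |
| 120 kg | 1.50 | 83.3% | 100% |
| 140 kg | 1.29 | 71.4% | 100% |

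If both the dose and the reference were 1.2 mg/kg, the percentages would be the same.

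**Rounding.** Rounding up by the full 5% gives 180 x 1.05 = 189 mg. At 105 kg this is 189/105 = 1.80 mg/kg, RDI 100%. At 110 kg RDI is 95.5% and at 120 kg 87.5%. Rounding can therefore hide the effect up to 105 kg and only soften it beyond.

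**Effect on a cohort mean.** The share of subjects above 100 kg is an assumption. The fall in mean RDI is share x (100 - RDI), taking those subjects as otherwise fully dosed.
- 10% at 120 kg: 0.10 x 16.7 = 1.7 points.
- 5% at 110 kg: 0.05 x 9.1 = 0.5 points.
- 30% at 140 kg: 0.30 x 28.6 = 8.6 points.

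**Weight change below the cap (secondary).** Both protocol sections require recalculation only around a 10% change in weight, though they word the trigger differently. A dose fixed at 80 kg is 144 mg. If weight moves without recalculation, SAP RDI is 144/72.1/1.8 = 111.0% at 72.1 kg and 144/87.9/1.8 = 91.0% at 87.9 kg. This error runs in both directions. It need not arise, because the protocol also lets sites adjust the dose for smaller changes under their own standards.

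**The case against.** **RDI is a minor, descriptive output.** This stands. It is not among the primary safety endpoints in protocol 8.3.1 or SAP 4.1. DLTs are defined by reductions, delays and discontinuation (SAP 7.6.1), not by RDI. The SAP also reports medians, which a few heavy subjects barely move, although one such subject can set the reported minimum.

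**A reader might infer that heavy, fully dosed subjects cannot be told apart from subjects reduced for toxicity.** At 150 kg the SAP formula does give 180/150 = 1.20 mg/kg and RDI 66.7%, which equals 1.2/1.8. The documents do not support the inference. SAP 7.4.2 tabulates reductions as the investigator reports them, with reasons. SAP 7.4.2.1 and 7.4.2.3 do the same for delays and discontinuations, and a by-subject dosing listing is planned. Only the RDI and mg/kg values can coincide. A subject reduced after a first full dose would not sit at 66.7% either: over eight on-time doses, (1.8 + 7 x 1.2)/14.4 = 70.8%. The weight range to 160 kg in protocol 1.1.13.2 comes from a pooled nivolumab data set and says nothing about this trial's weights.

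**A reader might infer that every subject above 100 kg must score below 100%.** That is too strong, given the rounding allowance.

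**Milligrams per actual kilogram is a legitimate measure of exposure.** This stands for cumulative dose: capping it would hide how little a heavy subject received per kilogram. It does not rescue RDI, which compares delivery with plan.

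**The RDI cell ends on the word *or* in the available text, so a second formula may be missing.** True, but the error arises in the per-kilogram dose definition, which is a separate and complete cell. A variant reference of 1.2 mg/kg would not correct it.

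**Conclusion.** The concern holds as a mismatch of definitions between the SAP and the protocol. For subjects above 100 kg on nominal full dose and on schedule, the SAP formula returns 100 x 100/weight instead of 100%. The size per subject is exact under those conditions: about 5 points lost at 105 kg, 9 at 110 kg, 17 at 120 kg and 29 at 140 kg. Doses rounded up within 5% lose less, or nothing up to 105 kg.

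The size per cohort is unknown because the documents give no weight distribution for this trial. The 1.7-point figure rests on an assumed 10% of subjects at 120 kg.

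The consequence is limited to the descriptive brentuximab exposure summaries. A reader might take the link to the safety objective to mean that a primary result is affected. It is not: ORR, its confidence interval, DLT counts and investigator-reported reductions do not use this quantity. The definition should still be corrected, because following it as written gives a wrong RDI.

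**What to change.** In SAP Table 7.4.1-1, compute brentuximab RDI as actual milligrams over the milligrams planned for the same period under the protocol dosing rule, cap included. Equivalently, use the smaller of weight and 100 kg as the divisor in the RDI numerator.

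Cumulative dose per actual kilogram can stay as a measure of exposure if it is labelled as such and is not fed into RDI.

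Where the weight used to calculate each dose is recorded, using it (capped) would also remove the smaller artefact from weight change within the 10% band. This is optional, since the table mentions only most recent weight as collected. If it is adopted, the differently worded recalculation triggers in protocol 4.3.1 and 4.5 must first be reconciled.

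The cost is one changed definition and a small programming change. Milligrams and weight are already on the CRF, and neither treatment nor data collection changes.

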First dose of nivolumab will be administered on Cycle 1 Day 8, which is only 2 weeks away from Cycle 2 Day 1. For safety reasons, subjects may be dosed no less than 12 days between doses. For all other cycles, treatment is to occur within 3 days of the scheduled dosing date. Dose given after the 3 day window is considered a dose delay. Treatment may be delayed for up to a maximum of 6 weeks from the previous dose. Refer to [Section 4.5.4](#) for further details.

Subjects will be monitored continuously for AEs while on study. Treatment modifications (eg, dose delay, interruption or discontinuation) will be based on specific laboratory and AE criteria (further details described in [Section 4.5.3](#) and [Section 4.5.4](#)).

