7.4.2 Modifications of Study Therapy

There will be no dose escalations or reductions of nivolumab allowed. Brentuximab Vedotin may reduce dose to 1.2mg/kg. Brentuximab. Dose reduction as reported by the investigator will be summarized along with reason for reduction.

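### The SAP's nivolumab relative dose intensity formula for two or more doses has an unclosed parenthesis and an ungrouped denominator, so it cannot be evaluated as printed, and adding only the missing parenthesis does not repair it

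*SAP*

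**What the plan says.** SAP 7.4.1 lists relative dose intensity among the exposure parameters to be summarized for each drug, and Table 7.4.1-1 gives the formulas. The table describes the nivolumab schedule as "Day 1, 240mg every 3 weeks (except cycle 1 C1D8").

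- **One nivolumab dose:** "Cum dose (mg)/[(Last dose date of nivolumab - Start dose date of nivolumab + 14) x 240 /14] x 100".
- **More than one nivolumab dose, first factor:** "Cum dose (mg) / (Last dose date of nivolumab - Start dose date of nivolumab + 21", with its brackets then closed.
- **More than one nivolumab dose, second factor:** after an opening square bracket and an opening parenthesis, "14+(number of nivolumab doses-1) * 21 / 240 * number of nivolumab doses] x 100".
- **Brentuximab vedotin, as far as the cell is legible:** "Cum dose (mg/kg)/[(Last dose date of BV - Start dose date of BV + 21) x 1.8 /21] x 100".

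Two other statements fix what the nivolumab formula should measure. Protocol 4.5 says: "First dose of nivolumab will be administered on Cycle 1 Day 8, which is only 2 weeks away from Cycle 2 Day 1". SAP 7.4.2 says: "There will be no dose escalations or reductions of nivolumab allowed".

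**The concern.** RDI compares the dose delivered per unit time with the dose planned per unit time, so a subject treated exactly to plan should score 100%. The second factor for two or more doses is evidently meant to be planned days divided by planned milligrams, but it has two faults. It opens two parentheses and closes one. And the slash is followed by 240 and then by a multiplication by the number of doses, with nothing to hold those two together as a denominator. Under ordinary operator precedence that divides by 240 and then multiplies by the number of doses.

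The practical risk is a partial repair. The unbalanced parenthesis stops a program from running, so it will be noticed. The ungrouped denominator will not stop it. Two programmers could patch the line differently, and one-dose subjects, whose formula is sound, would be summarized together with subjects whose values are not.

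**Working it through.** **Inputs.** Each dose is 240 mg with no change allowed (SAP Table 7.4.1-1 and 7.4.2). On schedule the first gap is 14 days (Protocol 4.5) and every later gap is 21 days. Let n be the number of nivolumab doses and D the days from first to last dose.

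**Benchmark.** The SAP gives no numerical RDI to reproduce, so I used its sound formulas as the standard.

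- One nivolumab dose: 240 / [(0 + 14) x 240/14] x 100 = 240/240 x 100 = 100%.
- Brentuximab vedotin, n doses on schedule at 1.8 mg/kg: 1.8n / [(21(n - 1) + 21) x 1.8/21] x 100 = 1.8n / 1.8n x 100 = 100%.

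**On-schedule subject, n of 2 or more.** D = 14 + 21(n - 2), so D + 21 = 14 + 21(n - 1). Call this S. Cumulative dose is 240n, and the first factor is 240n/S.

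**Both brackets supplied.** (240n/S) x [S/(240n)] x 100 = 100% for every n.

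**Literal string.** It has two opening parentheses and one closing, and returns a syntax error.

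**Missing parenthesis supplied, denominator left ungrouped.** For n = 2: S = 35, and the first factor is 480/35 = 13.714.

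- (A) Closed after 21: 35/240 x 2 = 0.2917, and 13.714 x 0.2917 x 100 = 400%. In general (240n/S) x (S/240) x n = n squared, that is, 100 x n squared %.
- (B) Closed at the end: 14 + 21/240 x 2 = 14.175, and 13.714 x 14.175 x 100 = 19,440%.
- (C) Closed after (n - 1): 15 x 21/240 x 2 = 2.625, giving 3,600%.
- (D) Closed after 240: (14 + 21/240) x 2 = 28.175, giving 38,640%.

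| n | S (days) | Both repaired | (A) after 21 | (B) at the end |
|---|---|---|---|---|
| 2 | 35 | 100% | 400% | 19,440% |
| 4 | 77 | 100% | 1,600% | 18,764% |
| 5 | 98 | 100% | 2,500% | 19,286% |
| 8 | 161 | 100% | 6,400% | 22,539% |

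None of these completions returns 100%; the smallest value is 400%.

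**The opposite partial repair.** Grouping only the denominator and leaving the numerator ungrouped gives, at n = 2, 14 + 21/480 = 14.04375, and 13.714 x 14.04375 x 100 = 19,260%. Both groupings are needed.

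**Sense check of the repaired formula.** Five doses with 21 days of total delay: D + 21 = 98 + 21 = 119, and RDI = 98/119 x 100 = 82.4%. It falls with delay, as it should.

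**The case against.** The strongest reply is that the intent is not in doubt. The constants 14, 21 and 240 match the schedule, and the quantity can be rebuilt from the documents alone. A string that will not run forces someone to look at it, and 400% or 19,440% for a subject treated to plan would be seen at once. That stands, and it makes a wrong published table less likely. It does not make the written rule correct.

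A second reply is that the table may have been damaged when the PDF text was extracted: it breaks mid-row, and the brentuximab cell ends at a dangling word. A stacked fraction would need no brackets around its denominator. This cannot be fully excluded, and the truncated brentuximab cell is not counted here as an error. But the slash and asterisks are inline characters, which makes a flattened fraction unlikely, and the one-dose formula in the same column kept its brackets.

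A reader might infer two stronger things:

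- *That the SAP formula itself yields several hundred to many thousand percent.* It does not: as printed it yields nothing. Each figure above depends on a bracket that the reader supplies, and the values have no fixed upper limit because they depend on its position and on n.
- *That every subject with two or more doses will receive a meaningless value, undermining the tolerability objective.* That assumes a wrong patch is made and accepted. RDI is also not among the primary safety endpoints in SAP 4.1. Nivolumab delivery is described independently by number of doses, cumulative dose and treatment duration (7.4.1), dose delays (7.4.2.1) and discontinuation of each drug (7.4.2.3), none of which uses this formula.

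**Conclusion.** The formula is wrong as written, in two places: an unclosed parenthesis and an ungrouped denominator. Repairing only the parenthesis leaves an on-schedule two-dose subject at 400% or 19,440% under the two most natural placements, where 100% is intended. Those figures assume ordinary operator precedence, 240 mg at each dose, and gaps of 14 days and then 21 days.

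The consequence is limited to the descriptive summary of nivolumab exposure. No response rate, confidence interval, DLT decision or listed primary safety endpoint depends on it. The line should be corrected before the exposure tables are programmed, but it does not threaten the trial's conclusions. The finding is subject to checking the source page for a bracket lost in extraction.

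**What to change.** In SAP Table 7.4.1-1, for n of 2 or more nivolumab doses, state:

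RDI (%) = 100 x [cumulative nivolumab dose in mg / (last nivolumab dose date - first nivolumab dose date + 21)] x [(14 + (n - 1) x 21) / (240 x n)]

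This keeps the SAP's own terms and adds only the missing grouping. Add a programming check that an on-schedule subject returns 100% at n = 2, 4 and 8. The cost is one line of SAP text and one check. No new data are needed, and no dosing rule changes.
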